To ensure fidelity to the study protocol and to avoid any perceived coercion by JJ staff, TCU Institute of Behavioral Research (TCU/IBR) RAs will oversee intervention administration, including voluntary study enrollment and withdrawal if requested. Following our NIDA-funded JJ- TRIALS study protocol, NO participant information (youth participation, youth assessment responses, choices/responses selected during the intervention, completion of sessions) will be shared with JJ staff; only aggregate information will be shared with JJ leadership.

11. Location:

All intervention and assessments sessions will take place either online using a platform such as Zoom, in-person at a Tarrant County Juvenile Services office or another public place, or via a tablet hand-off in an agreed upon public place. All TCU rules and regulations regarding COVID-19

protocols will be followed for in-person interactions including masking, hand-washing/sanitizing, social distancing when able, and sanitizing of all equipment.

12. Subject Population:

Participants will include juvenile justice-involved youth on probation within at least 1 local juvenile probation department (Tarrant County, currently). The Tarrant County Board (TCJS) has granted preliminary approval to submit appropriate requests to TJJD to move forward with planning this study.

We expect to recruit approximately 60 youth who range in age from 14 to 18 years old.

Inclusion Criteria: Youth ages 14-18 on community supervision are eligible if they have 1 or more indicator(s) of substance use, are English-speaking, and have no indication of current suicide risk or severe cognitive impairment/thought disorders. Youth's parent/legal guardian may be Spanish-speaking. Upon approval of the parental consent document, it will be translated into Spanish and submitted to the IRB for approval.

Exclusion criteria: Youth who are on TJJD (state) supervision rather than county supervision are not eligible to participate. In addition, youth who are currently suicidal, homicidal, or otherwise severely impaired (e.g., active psychotic symptoms) such as severe cognitive impairment or thought disorders are not eligible. Youth younger than 14 and youth 19 or older are likewise not eligible.

13. Recruitment Procedure:

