Prior to study start, TCU will meet virtually with TCJS leadership to finalize recruitment, compensation, study implementation, and sharing of youth records. The TCJS Director of Research (DOR) will work directly with TCU and TJJD to ensure that data sharing agreements and procedures for linking study data to youth records are appropriate and secure. For study management purposes providing incentives to families, the DOR will know which youth are participating in the study but will keep this information confidential; supervising officers will not have access to this information. Information shared between the DOR and research team will be retained in and shared via a Box (account owned by TCU) folder with access restricted to the DOR and research team. Prior to participant recruitment, RAs will be trained on the general study protocol (e.g., recruitment, eligibility, consenting), curriculum content (e.g., rationale, content, exercises), delivery strategies, tablet operation, web access (e.g., troubleshooting, technical problem resolution), and how to address sensitive issues. RAs will be trained on identifying symptoms of trauma, handling information disclosed by youth, and will follow specific procedures required by the JJ department for reporting abuse or trauma to health personnel.

We will work with departmental staff to develop recruitment and administration procedures, including identifying the best group(s) from which to recruit participants and troubleshooting options for youth with challenges such as lack of access to Wi-Fi.

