As part of supervision orientation procedures, JJ Probation Officers will distribute and/or e-mail flyers (see Appendices 3-4) describing the study to youth under community supervision and their parents/guardians. The flyer will describe the project (purpose, time commitment, compensation, benefits, eligibility criteria), and provide contact information for the research study. They will also give a brief description of the study to the youth and their caregivers, and ask for permission to share the youth and caregiver's contact information with the TCU research team. If they agree, the information will be conveyed using either a spreadsheet or Qualtrics link with the clients PID number, basic demographics, contact information for youth and caregiver, and eligibility criteria. The youth and/or caregiver will contact the study team from TCU if interested or the RA will reach out to families that agree to share their contact information. The RAs will set up an initial virtual or in-person session to evaluate the family's interest, screen for eligibility, and consent/assent. The project ends 8/31/22. All sessions that occur prior to 8/31/22 will be compensated.

14. Consenting Procedure:

The TCU RA will contact the client and family via phone or e-mail to schedule a time for the consent/assent session that is convenient to the family. The RA will reach out to the families via email and text messages

Consent and study sessions will either occur virtually, in-person, or via a tablet hand-off in a public place. A courtesy reminder e-mail and text message providing the information about the session will be sent 3 days prior, 1 day prior and a few hours prior the session with the prepared scripts. The RA will meet individually via a virtual platform or in-person with only those who express interest, screen the youth for eligibility and describe the study.

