To request corroborating data from the local JJ department as well as the Texas Department of Juvenile Justice (TJJD), the research team will request that the TCJS research director provide the TJJD-based identification number (PID) for consenting participants as well as demographic, substance screening and assessment, and relevant service attendance information. These data will be shared via a spreadsheet available to the director of research and the research team via Box.com – a secure file-sharing platform. The research team will provide the PID numbers along with headquarters county ID to the TJJD data team via spreadsheet in a Box folder in return for state-level data specific to the youth's substance use screening and assessments as well as offense, background, and service-seeking data. The TJJD research proposal submitted in September 2020 can be found in Appendix 9. be found in Appendix 9.

Intervention

The youth will receive 4 sessions of the interactive, cloud-based intervention administered via a tablet we give them. Each session of the intervention will focus on one of topics associated with drug use and risky sex practices. The final session will include an integrated module ensuring that youth process through a scenario that examines how drug use and risky sex behaviors are related. The youth will complete the final WORK-IT scenario within the app with processing questions (see Appendix 5.7) to work through this integrated scenario and also a quiz-like activity on Kahoot to learn more about local resources for substance use and sexual health.

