Probable: SAE is likely related to the intervention Possible:
SAE may be related to the intervention Unlikely: SAE is
doubtfully related to the intervention Unrelated: SAE is
clearly not related to the intervention

Participants' descriptions of adverse events (incident reports) will be grouped in a reasonable way, counted, and compared by study groups. A designation of "more-common" will be given to events occurring at an incidence of at least 5% in participants assigned to an intervention group, and for which the incidence is at least twice that observed in a comparison group. Staff will be trained to carefully observe participants' reactions to the study protocol and to take appropriate action including support, discontinuance, or referral to additional counseling services, if necessary. Based on previous experience and the current use of these TCU materials with other IRB research projects we have found that such occurrences are rare.

Reporting Timeline

SAEs will be reported to the PI within 24 hours of detection. Within 3 business days, the PI will send a full report on the SAE, including the action taken with regard to continued study participation to the IRB. Non-serious AEs or adverse effects that lead to subject removal from the protocol will be reported to the IRB within 7 business days. The PI will maintain a record of the SAEs, which can be provided to the IRB electronically. The outcome of SAEs also will be reported to NIDA in annual reports. A summary of the SAEs and AEs that occurred during the previous year will be included in the annual progress report to NIDA.

17. Potential Benefits:

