Implementation feasibility measures will be recorded, summarized, and reviewed monthly by the PI and team in order to inform real-time protocol adjustments (e.g., changes in recruiting practices if target numbers are not reached). Once the targeted youth recruitment goal has been achieved, psychometric properties of baseline measures will be conducted (means, SD, coefficient alpha, exploratory/confirmatory factor analysis). Because the design calls for repeated measures at baseline, month 1, and month 3, measures will not be revised between administration points.

However, psychometrics (conducted on data from all time points) will be used to inform modifications prior to a full-scale R01 RCT and reliability of scales for use in exploratory analyses of intervention efficacy.

Baseline characteristics will be included as covariates in analyses. The distal outcome will be the percent of study subjects who use drugs (self-report, corroborated with positive urine test) at follow-up (1- and 3-months). All study participants (regardless of study retention) will be included in analyses (i.e., an intent-to-treat approach; ITT). Baseline variables that directly relate to our aims (e.g., drug use, risky sex practices) will be evaluated for use as covariates. Abstinence at each

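### Section 20 names no comparator for drug use in youth who all receive the app under supervision, yet speaks of a treatment effect and sizes the R01 from it

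*Combined protocol and SAP*

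**What the plan says.** **Who is studied.** Section 12: "Youth ages 14-18 on community supervision are eligible if they have 1 or more indicator(s) of substance use". It sets no limit on time under supervision, and current or ordered SU treatment is not an exclusion. The target is: "We expect to recruit approximately 60 youth who range in age from 14 to 18 years old".

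**How they are reached.** Section 13: "As part of supervision orientation procedures, JJ Probation Officers will distribute and/or e-mail flyers". The same section leaves open the task of "identifying the best group(s) from which to recruit participants".

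**What they receive.** Section 15: "The youth will receive 4 sessions of the interactive, cloud-based intervention administered via a tablet we give them". No randomisation or control arm is described. The monitoring plan in Section 16 flags adverse events "for which the incidence is at least twice that observed in a comparison group", but that group is not defined anywhere. The Summary says the app includes a referral component and lists service initiation among the proximal outcomes.

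**What is collected.** Section 15 asks the county for "relevant service attendance information", along with demographic and substance screening data. It asks the state agency for offense, background and service-seeking data.

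**What is analysed.** In Section 20 the distal outcome is the percentage using drugs at 1 and 3 months. Abstinence at each follow-up is tested by chi-square. Unlisted baseline characteristics are to be covariates, and "Baseline variables that directly relate to our aims (e.g., drug use, risky sex practices) will be evaluated for use as covariates". Receipt of SU services is a dichotomous proximal outcome. The efficacy analyses are called exploratory. The text on multiple imputation nevertheless refers to unbiased estimates of a treatment effect, and effect sizes are to be used to size the R01.

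**The concern.** With one treated group and no comparator, the natural reading of the chi-square test is baseline against follow-up. A change measured that way is the sum of everything that happened to these youth over the interval: the app, supervision itself, and any SU service they were already attending. Section 20 does not say that the result is such a sum. It describes the result in the language of a treatment effect and passes it to the next trial.

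The imputation sentence does not help. Multiple imputation under missing-at-random deals with absent outcome values. It cannot supply the missing comparison, so it cannot make a pre-post change an unbiased estimate of what the app did.

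Two things are at stake. A fall in drug use could be reported as promise of efficacy when the app contributed little or nothing. The R01 could also be planned around an effect much larger than a randomised comparison would show.

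**Working it through.** **1. Figure to reproduce.** There is none. The target of about 60 has no alpha, power, rates or effect size behind it. Everything numerical below is illustration on assumed values.

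**2. The sections side by side.**
- Section 15 gives the app to everyone described, so no concurrent group shows what would have happened without it.
- Section 12 allows youth already in SU services, so those services can act between baseline and follow-up.
- Section 20 uses services only as an outcome and does not relate drug use to services already under way at baseline.
- Section 20 does not name the comparator of the chi-square test, and that test takes no covariates.
- A covariate model would not remove the problem either: a change shared by all members of a single group cannot be separated from the app by baseline adjustment.

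**3. How large could a background fall be?** Assume 60% use at baseline: 0.60 × 60 = 36 users. Assume one third (20 youth) are in other SU treatment at baseline and that it halves their use: 20 × 0.60 = 12 falls to 6. Total use becomes 30/60 = 50%, a 10-point fall with no app effect. Assume also that supervision lowers use by 10 to 20 points in the other 40 youth (4 to 8 fewer users). The total becomes 26/60 = 43.3% or 22/60 = 36.7%, a fall of 16.7 to 23.3 points. If treatment had already done its work before baseline and supervision has no effect, the background fall is 0. The range on these assumptions is therefore 0 to about 23 points.

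**4. How often would that look like an effect?** Simulation of paired binary data: true app effect zero, baseline use 50% or 70%, latent correlation 0.5, 2000 runs per setting, two-sided 0.05. The second sample size assumes 20% loss (60 × 0.8 = 48).

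| Background fall | Chi-square, N=60 | Exact McNemar, N=60 | Chi-square, N=48 |
|---|---|---|---|
| 0 points | about 2% | 2–4% | 1–2% |
| 10 points | 15–16% | 20–21% | 11–13% |
| 20 points | 64% | 70% | 51–54% |
| 30 points | 96–97% | 97–98% | 90–93% |

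The top row shows that the test itself is not too liberal. The lower rows reflect a real change that is not due to the app.

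**5. What happens to the R01?** Sample size per arm, two-sided 0.05 and 80% power, with p̄ the mean of p1 and p2:

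n = [1.96·√(2p̄(1−p̄)) + 0.8416·√(p1(1−p1) + p2(1−p2))]² / (p1−p2)²

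- The whole 20-point fall is taken as the app effect (50% vs 30%): (1.3579 + 0.5708)² / 0.04 = 93 per arm. The pair 70% vs 50% gives the same.
- Only 10 of the 20 points are due to the app: 40% vs 30% needs 356 per arm and 60% vs 50% needs 388. A trial with 93 per arm has 28–30% power.
- Only 5 of the 20 points are due to the app: 35% vs 30% needs 1377 per arm and 55% vs 50% needs 1565. A trial with 93 per arm has 10–11% power.

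**The case against.** The strongest reply is that this is a feasibility pilot. Pilot 2's aim is protocol feasibility, full testing is left to a later RCT, and the efficacy analyses are labelled exploratory. That stands as a limit on severity. It does not protect a number that is carried into a sample-size calculation.

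Several stronger readings are tempting, and the documents do not support them.

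- *A reader might infer that the plan ignores services and supervision.* It does not. Services are collected and analysed as a proximal outcome, and the open phrase about baseline characteristics could cover time on supervision or prior treatment. These are unspecified, not excluded.
- *A reader might infer that baseline sits at the start of probation.* Orientation is the stated flyer route, but eligibility is not limited to new supervisees and the recruitment groups were still to be settled. The interval is unknown.
- *A reader might infer that background change will be credited to the app.* The documents support only that it can be. Neither its size nor its direction is given.
- *A reader might want extra covariates, or the estimate in youth with no other SU service during follow-up, as the remedy.* Covariates cannot remove a shared change. The app is meant to prompt service use, so services begun after baseline may be one of its effects. Selecting youth without them would discard part of any benefit and leave a self-selected subgroup.
- *A reader might take the one-third treated share as evidence.* In Section 10 that figure is an annual one for justice-involved youth with SU disorders. Entry here requires only one SU indicator, so the share is an assumption and nothing more.

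It is also fair to say that the records may not be complete for this purpose. Section 15 lists service attendance but not treatment orders, and no supervision start date is named.

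**Conclusion.** The concern holds in a limited form. Section 20 defines no comparator for the abstinence test in a group that all receive the app under supervision, and it does not separate SU services already under way at baseline. It nevertheless describes a treatment effect and uses effect sizes for the R01. Followed as written, the plan allows background change to be read as the app's doing.

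The size cannot be determined from the documents. On the assumed rates above, a 10- to 20-point background fall would be significant in about 15% to 64% of trials of 60 by chi-square with no app effect. An R01 planned from a 20-point fall would drop from 80% power to about 28–30% if half of it belonged to the app. These figures assume a baseline-versus-follow-up test, 50–70% baseline use and, for the simulation, a latent correlation of 0.5. If a comparison group does exist, as the adverse-event wording hints, it has to be defined before any of this can be reassessed.

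**What to change.** In Section 20:

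1. State the comparator of the chi-square test. If it is baseline versus follow-up, call the result pre-post change under supervision plus usual services, and remove the reference to a treatment effect.
2. From the agency records already requested, tabulate drug use at baseline, month 1 and month 3 by SU-service status at baseline. If the date can be obtained, tabulate also by time since supervision began. Label both as description only.
3. Report services begun after baseline separately, as the proximal outcome they already are. Do not adjust drug use for them, and do not present youth without other services as showing the app's effect.
4. Do not size the R01 from the uncontrolled change alone. The pilot can still inform baseline prevalence, retention and within-youth correlation. If the observed change is used at all, show the required size over a range of shares due to the app, as in step 5 of the working.

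The cost is a few lines of text, one extra table with small subgroups that can only be described, and possibly one added date field in the county spreadsheet. The team also accepts a less favourable reading of any fall in drug use.

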follow-up time point will be compared using chi square test. Our proximal outcomes will include putative measures (e.g., problem recognition, decision making, intention to reduce personal risk) and receipt of SU services (dichotomous measure from youth records). Because proportions of females and their SU rates are generally lower among JJ youth compared to males,⁶ and males/females may respond differently to MEC interventions,¹⁶ we will explore sex (as a biological variable) differences in SU, risky sex practices, and exploratory outcomes using univariate analyses (e.g., chi square, t-tests, ANOVA). We will also explore potential racial/ethnic disparities in order to more fully inform whether cultural modifications are needed for a subsequent application. A log rank test will be used to assess intervention dropout. Participants who withdraw consent or are lost to follow up will be missing on outcome measures. To address this, stochastic multiple-imputation will be attempted, which will provide maximum likelihood estimates, account for uncertainty in missing values, and provide unbiased estimates of the treatment effect if data are missing at random. Effect sizes will be used to calculate sample sizes needed for the larger R01. Calculations will include samples needed to assess intervention feasibility across sex and race/ethnicity subgroups.

21. Check List for the Items That Need to be Submitted:

a. Protocol	
b. Consent document	
c. HIPAA form if applicable	
d. Protecting Human Research Participants Training certificate for each investigator	
e. Recruitment flyers, letters, ads, etc.	
f. Questionnaires or other documents utilized in screening and data collection	

Principal Investigator Assurance

22. By signing below, I certify to the following:

- The project described herein will be conducted in accordance with applicable TCU policies and procedures, as determined by the IRB of record. All Human Subject Research projects occurring at TCU must be conducted in compliance with the Office of Human Protection ("OHRP") regulations at 45 CFR 46 and all other applicable federal and state laws and regulations (collectively "Applicable Law")
- I have a working knowledge of Applicable Law

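### The chi-square test named for overall abstinence has no stated comparison; in a one-group pilot the available comparison is within youth, where the test ignores pairing, loses power and omits the promised covariates

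*Combined protocol and SAP*

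**What the plan says.** Section 20 defines the outcome: "The distal outcome will be the percent of study subjects who use drugs (self-report, corroborated with positive urine test) at follow-up (1- and 3-months"). It then says abstinence at each "follow-up time point will be compared using chi square test". No other test is named for overall abstinence. The only other tests that touch substance use are exploratory univariate comparisons by sex.

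The same section makes three commitments that bear on that test:

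- **Repeated measures.** "Because the design calls for repeated measures at baseline, month 1, and month 3, measures will not be revised between administration points".
- **Covariates.** "Baseline characteristics will be included as covariates in analyses". A later sentence is weaker: baseline drug use and risky sex practices are to be evaluated as possible covariates. No regression model is named.
- **Missing data.** Everyone is analysed whatever their retention, and "stochastic multiple-imputation will be attempted, which will provide maximum likelihood estimates". No imputation model or pooling rule is given.

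On the design, Section 12 says "We expect to recruit approximately 60 youth who range in age from 14 to 18 years old", and Section 15 (Intervention) says "The youth will receive 4 sessions of the interactive, cloud-based intervention administered via a tablet we give them". Sections 12 to 15 contain no randomisation, allocation or control condition.

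Some wording elsewhere points to groups. The safety plan in Section 16 would label an adverse event as more common where it is frequent enough and "for which the incidence is at least twice that observed in a comparison group". Section 20 mentions an unbiased treatment effect and intent-to-treat analysis.

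**The concern.** A comparison needs two things to compare, and the chi-square sentence supplies only the outcome and the visits. In a single cohort, overall abstinence can be set against abstinence at another visit in the same youth. An ordinary Pearson chi-square treats the two sets of answers as coming from different people. When a youth's answers are positively correlated, that overstates the uncertainty of the change, and real change is easier to miss.

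The test also has no place for covariates, so the adjustment promised a few lines earlier would either not reach the distal outcome or have to be added through a model the plan does not name.

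These results matter beyond the pilot, because Section 20 uses the effect sizes to plan the sample size of the larger trial.

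**Working it through.** **Inputs from the documents.** About 60 youth (Section 12); a binary outcome; visits at baseline, month 1 and month 3 (Section 20); one group (Section 15). The documents give no alpha, abstinence rate, within-youth correlation, dropout rate or power target, so there is no planned figure to reproduce.

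**Assumptions.** Two-sided 5% level; 60 complete pairs; within-youth correlation ρ of 0, 0.3, 0.5 or 0.6; abstinence 40% to 55% as the main illustration.

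**Step 1: standard error of the change.** With p₁, p₂ the abstinence proportions at two visits and q = 1 − p:

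- Unpaired: √[(p₁q₁ + p₂q₂)/N]
- Paired: √[(p₁q₁ + p₂q₂ − 2ρ√(p₁q₁p₂q₂))/N]

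When p₁q₁ and p₂q₂ are equal or nearly so, the ratio is 1/√(1 − ρ): 1/√0.7 = 1.20, 1/√0.5 = 1.41, 1/√0.4 = 1.58. The overstatement is about 20%, 41% and 58%.

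For 40% to 55%, p₁q₁ = 0.24 and p₂q₂ = 0.2475. The unpaired SE is √(0.4875/60) = 0.090. At ρ = 0.5 the paired SE is √[(0.4875 − 0.2437)/60] = 0.064. The 95% half-widths are 1.96 × 0.090 = 17.7 and 1.96 × 0.064 = 12.5 percentage points.

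**Step 2: true size at nominal 5%.** By normal approximation this is 2[1 − Φ(1.96/√(1 − ρ))]. For ρ = 0.3 / 0.5 / 0.6 the argument is 2.34 / 2.77 / 3.10, giving 1.9% / 0.6% / 0.2%. Simulation at 50% in both visits gives about 2% / 0.7% / 0.3%.

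**Step 3: power, by simulation of 60 pairs** (McNemar without continuity correction; good to about one percentage point):

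| Abstinence (assumed) | ρ | Pearson, pairing ignored | McNemar |
|---|---|---|---|
| 40% to 55% | 0.3 | 37% | 51% |
| 40% to 55% | 0.5 | 35% | 64% |
| 40% to 55% | 0.6 | 33% | 74% |
| 30% to 50% | 0 | 62% | 61% |
| 30% to 50% | 0.3 | 64% | 77% |
| 30% to 50% | 0.5 | 66% | 90% |
| 30% to 50% | 0.6 | 68% | 97% |

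With 48 pairs (assumed 20% loss), 30% to 50% and ρ = 0.5, the figures are 52% and 81%. The exact McNemar test gains less: for 60 pairs and 30% to 50% it has 52% / 69% / 85% / 94% power at ρ = 0 / 0.3 / 0.5 / 0.6.

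**Step 4: the between-group reading.** If two separate groups existed and were compared visit by visit, each youth would appear once per table. For an illustrative 30 against 30 the simulated size is 4.8% to 5.2%, so the test would hold its level.

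**Step 5: covariates.** A plain Pearson chi-square on a two-way table has no covariate term. This holds on either reading.

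**The case against.** **The across-visit reading is an inference.** Taken literally, the sentence describes one comparison per follow-up visit, with one answer per youth, and Step 4 shows that independence would then hold. The references to study groups, a comparison group and a treatment effect lean the same way. This stands as far as it goes. It needs a second group, however, and the procedures describe none. On that reading the comparator is undefined and the covariates are still left out.

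**A reader might infer that a chi-square cannot be used with multiple imputation.** That is not so. Chi-square statistics from imputed data sets can be combined by the D2 rule, and risk differences by Rubin's rules. In a simulated example with 9 of 60 outcomes missing and 20 imputations, D2 gave F = 0.39, p = 0.53; the Rubin SE was 0.137, against 0.124 without between-imputation variance. What is missing is a stated pooling rule.

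**A reader might also infer that the p-values and intervals will be wrong whatever is compared.** The documents do not support that. The error arises only if visits are compared. With positive correlation it costs power and does not create false positives. The test itself produces no interval.

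**The magnitude is assumed throughout.** This stands. The higher correlations are not always attainable, either. The largest possible correlation is √[p₁q₂/(q₁p₂)] when p₁ < p₂. Eligibility requires an indicator of substance use, so baseline abstinence could be low. If it went from 10% to 40% (assumed), the ceiling would be √[(0.1 × 0.6)/(0.9 × 0.4)] = 0.41. For 40% to 55% it is √[(0.4 × 0.45)/(0.6 × 0.55)] = 0.74, so the values tabulated are possible there.

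**The consequences are limited.** Pilot 2 is about protocol feasibility, and Section 20 calls the efficacy analyses exploratory. On the same data, the observed difference in proportions is identical under chi-square and McNemar, so the choice of test does not bias the effect estimate passed to the larger trial. This bears on severity. It does not supply the missing comparison or the adjusted model.

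**Conclusion.** The point holds in a limited form and should be fixed. It does not undermine the pilot's feasibility aims.

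Three things rest on the documents alone: the abstinence comparison is not defined, the named test cannot carry the promised covariates, and no paired or longitudinal method is named although the design is described as repeated measures.

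The loss of precision is conditional. It assumes that visits are compared within youth, which is the overall comparison the described design offers, and that repeated answers are positively correlated. For correlations of 0.3 to 0.6, the unpaired analysis overstates the standard error by about 20% to 58%, and its true size is about 2% down to 0.3% at nominal 5%. For a rise from 40% to 55%, it gives up about 14 to 41 percentage points of power to McNemar (51 − 37 = 14; 74 − 33 = 41). At zero correlation the loss disappears.

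**What to change.** Replace the chi-square sentence in Section 20 with text to this effect:

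- **Comparison.** Change in drug use (yes/no) within youth, from baseline to month 1 and from baseline to month 3.
- **Model.** One repeated-measures logistic model (GEE with robust standard errors, or mixed logistic) with time as a factor.
- **Covariates.** Named baseline characteristics other than baseline drug use. Baseline drug use is already an outcome row and must not also appear as a covariate.
- **Missing data.** State the imputation model, fit the analysis model in each imputed data set, and pool by Rubin's rules.
- **Reporting.** Change in percent using, with 95% CI, and McNemar on observed pairs as a simple check.

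This makes the pre-post comparison an explicit choice and adds baseline to an outcome that Section 20 defines at follow-up only; the text should say so.

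If a comparison group does exist, define it and how youth enter it, and use logistic regression at each follow-up adjusted for baseline drug use. Either way, reconcile the wording on study groups, a comparison group and a treatment effect in Sections 16 and 20 with the one-group design in Sections 12 to 15.

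The cost is a few lines of text and a little more analysis work. No new data or participants are needed.
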